7.6.2 Analysis of Adverse Events

A Medical Monitor will review events related to primary and secondary safety endpoints as they are reported. Events of Interest related to Symptomatic Intracranial Hemorrhage and Ischemic Stroke will also be reviewed by the medical monitor. Redacted source documents may be collected for events where the medical monitor deem necessary.

7.6.2.1 Definitions

- **Adverse Event (AE):** any untoward medical occurrence, unintended disease or injury, or untoward clinical signs (including abnormal laboratory findings) in subjects, users or other persons, whether or not related to the study medical device.
- **Adverse Device Effect (ADE):** An adverse event related to the use of the study medical device.
- **Definition of SAE**
An SAE is an event that:
 - Led to death
 - Led to a serious deterioration in the health of the patient that:
 - Resulted in life-threatening illness or injury
 - Resulted in chronic disease
 - Resulted in permanent impairment of a body structure or a body function
 - Required in-patient hospitalization or prolongation of existing hospitalization
 - Resulted in medical or surgical intervention to arrest permanent impairment to body structure or a body function
 - Led to fetal distress, fetal death or a congenital abnormality or birth defect
- **Unanticipated Adverse Device Event (UADE):** An unanticipated adverse device effect is any serious adverse effect on health or safety or any life-threatening problem or death caused by, or associated with, a device, if that effect, problem, or death was not previously identified in nature, severity, or degree of incidence in the protocol, or instructions for use. Unanticipated adverse device effect also includes any other unanticipated serious problem associated with a device that relates to the rights, safety, or welfare of subjects.

7.6.2.2 Relationship to the Study Device

An AE is considered to be device-related when it is reasonable to believe that the event may have been caused by or is related to the device. The following definitions will be used to assess the relationship of the adverse event to the use of study device. Grading for relatedness of ‘probable’ or ‘definite’ will be considered device related.

- **Definite:** The temporal sequence is relevant and the event abates upon device application completion/removal, or reappearance of the event on repeat device application
- **Probable:** The temporal sequence is relevant or the AE abates upon device application completion/removal or the AE cannot be reasonably explained by the subject’s condition or comorbidities. The AE is related or most likely associated with the device
- **Possible:** The temporal sequence between the device and the AE is such that the relationship is not unlikely or there is no contradicting evidence that can reasonably explain the subject’s condition. There is a possibility of a relationship between the AE and the device
- **Unrelated:** The AE is not associated with the device. There is no relation between the AE and the device

Similar grading will be used for assessing the relationship to index procedure, target aneurysm, and comorbidities.

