10.1 Primary Safety Analysis

For the primary safety endpoints, frequency counts, percentages, and two-sided 95% Wald confidence intervals will be reported using the ITT population:

- **SAEs up to 24 hours post-procedure:** The percentage of patients who experience serious adverse event(s) with start date on the date of procedure (day 0) or the next calendar day.
- **Device-related SAE up to 7 days or discharge:** The percentage of patients who experience serious adverse event(s) with probable or definite relationship to the SMART Coil System from the date of procedure (day 0) through the date of discharge or seven calendar days from the date of procedure, whichever occurs earlier.

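### The criteria for 'Probable' and 'Possible' device-relatedness overlap at the line that decides whether an SAE counts in a primary safety endpoint, and sites' grades are final

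*Combined protocol and SAP*

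**What the plan says.** Protocol 7.6.2.2 gives a general test, a cut-off and four grades.

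- General test, with the device as its object: "An AE is considered to be device-related when it is reasonable to believe that the event may have been caused by or is related to".
- Cut-off, later in the same paragraph: "Grading for relatedness of ‘probable’ or ‘definite’ will be considered device related".
- For the grade 'Definite', the criteria read: "The temporal sequence is relevant and the event abates upon device application completion/removal, or reappearance of the event on repeat device application".
- For the grade 'Probable', they read: "The temporal sequence is relevant or the AE abates upon device application completion/removal or the AE cannot be reasonably explained" (with reference to the subject's condition or comorbidities). This grade closes with: "The AE is related or most likely associated with the device".
- For the grade 'Possible', they read: "The temporal sequence between the device and the AE is such that the relationship is not unlikely or there is no contradicting evidence" (meaning evidence of another reasonable account of the subject's condition). This grade closes with: "There is a possibility of a relationship between the AE and the device".
- The last grade, 'Unrelated', means no association with the device.

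The analysis sections follow the cut-off. SAP 10.1 defines the primary endpoint, up to 7 days or discharge, as patients with "serious adverse event(s) with probable or definite relationship to the SMART Coil System". SAP 10.2 uses the same two grades for the secondary endpoint at final follow-up, and protocol 10.11 uses them for the adverse event analysis.

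SAP 10.3 says that there is no clinical events committee and that events are reported on the sites' assessment. Protocol 7.6.2 has a medical monitor review events related to the safety endpoints, but does not say that the monitor may change a site's grade.

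**The concern.** The paragraph sets two thresholds. Under the general test, an event that might have been caused by the device is device-related. Under the cut-off, an event graded only 'Possible' is not.

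The line between 'Possible' and 'Probable' decides whether an SAE enters the numerator, and the criteria listed on either side of it do not exclude each other. With grading spread over up to 60 sites and no central adjudication, two sites could grade the same event differently and each point to the text in support. At stake are one of the two primary safety endpoints and one secondary safety endpoint. The general test can also affect which events sites treat as device-related for the 72-hour reporting requirement in protocol 7.6.1.

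**Working it through.** **1. The plan's own figure.** Inputs are 22 events in 800 patients and a two-sided 95% Wald interval (protocol 10.2; SAP section 2).

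- p = 22/800 = 2.75%
- half-width = 1.96 × √(0.0275 × 0.9725 / 800) = 1.13 points
- interval = 1.62% to 3.88%

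This reproduces the stated 1.6% to 3.9%. The planning arithmetic is sound; the question is what enters the numerator.

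**2. The two grades side by side** (protocol 7.6.2.2).

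| | 'Probable' (counted) | 'Possible' (not counted) |
|---|---|---|
| Timing | relevant | makes a relationship not unlikely |
| Abatement | abates on completion or removal | not mentioned |
| Other explanation | not reasonably explained by condition or comorbidities | no contradicting evidence that reasonably explains the condition |
| How joined | any one suffices | either one suffices |
| Closing judgement | related, or most likely so | a relationship is possible |

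Two kinds of event meet the listed criteria of both grades:

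- An SAE with relevant timing and nothing else. It meets the first limb of 'Probable', and its timing would ordinarily also make a relationship not unlikely.
- An SAE with no other explanation and nothing else. It meets the third limb of 'Probable' and, in nearly the same terms, the second limb of 'Possible'.

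Only the closing judgements separate the grades. No hierarchy or tie-break says whether the criteria or the closing judgement governs.

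**3. Where the overlap matters.** 'Definite' and 'Probable' also overlap, but both are counted, so the rate is unaffected. The Probable/Possible line is the one that moves the rate.

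**4. What the plan does about it.** The sensitivity analyses in SAP section 12 impute missing data; none varies the relatedness cut-off. SAP 10.3 plans adverse event counts by relationship to device and procedure, with listings that include causality. It does not commit to a rate with a confidence interval that includes 'Possible' for either endpoint.

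**5. Illustration of size.** The documents do not give the number of SAEs graded 'Possible', so the net number of patients moved across the line is an assumption. With n = 800:

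- Upward: 31/800 = 3.875% is still within the planned 3.9%; 32/800 = 4.0% is outside it. Shift = 32 − 22 = 10 patients.
- Downward: 13/800 = 1.625% is still within the planned 1.6%; 12/800 = 1.5% is outside it. Shift = 22 − 12 = 10 patients.

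A net shift of 10 patients (10/800 = 1.25%) in either direction puts the point estimate outside the planned interval.

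**The case against.** The strongest reply is that the analysis rule is not ambiguous. Every place that defines the count uses probable or definite. The closing sentences give graders a usable distinction, and timing alone does not make an event most likely due to the device. Sites also grade the relation to the index procedure, target aneurysm and comorbidities, so early SAEs have other attributions available. A medical monitor reviews endpoint events.

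Much of this stands, and it rules out four stronger readings that a reader might infer:

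- *The opening sentence changes which grades are counted.* It does not. An event recorded as 'Possible' stays out of the numerator. The sentence can act only through how sites grade and what they report.
- *The reported rate is the most favourable reading.* The documents do not support a direction. Excluding 'Possible' lowers the rate, while a literal reading of the 'or' in 'Probable' raises it.
- *The rate could approach the 8.9% (71/800) planned for all SAEs by 24 hours.* That needs the 22 device-related events to lie within the 71, although the two endpoints have different windows. It also needs timing alone to suffice for 'Probable', against that grade's closing sentence.
- *The 'Definite' wording loses events.* Its tests of removal and repeat application fit a permanently implanted coil poorly, but an event that misses 'Definite' can still be counted as 'Probable'.

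What the reply does not remove is the overlap in the listed criteria. The closing sentences separate the grades by judgement only, that judgement rests with the sites, and no one is given stated authority to reconcile it.

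**Conclusion.** The point holds as a weakness in the grading rule, not in the analysis cut-off. Protocol 7.6.2.2 contains two thresholds for device-relatedness, and its criteria for a counted and an uncounted grade overlap. An SAE with the same facts can therefore enter or miss the numerator of the primary device-related endpoint, and of the secondary endpoint at final follow-up, depending on the site.

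That conclusion rests on the text alone and is firm. The effect on the rate is not: its direction is unknown, and its size cannot be computed from the documents. The 10-patient shift shows how few reclassifications would matter against the planned precision; it does not predict how many will occur. The correction is worth making because it is cheap and concerns a primary endpoint.

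**What to change.** In protocol 7.6.2.2:

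- Align the opening sentence with the probable/definite cut-off, so that one statement defines device-related.
- Make 'Probable' and 'Possible' mutually exclusive, so that relevant timing alone does not suffice for 'Probable'.
- Optionally, tidy the 'Definite' wording so that it can be applied to a permanent implant. This does not affect the rate.

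In SAP 10.1 and 10.2, keep probable/definite as the primary count. For each device-related endpoint, add one prespecified sensitivity row, with 95% confidence interval, that counts possible, probable and definite.

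The cost is wording in one protocol section and one table row per endpoint, using grades that 7.6.2.2 already defines. There are two downsides. A second rate is shown that can only be equal or less favourable. And if events have already been graded, which the documents do not state, new wording applies only going forward unless they are re-graded, so early and late patients could be graded under different rules. The sensitivity row is feasible either way and can be added before the SAP is signed off ahead of database lock.

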7.6.3 Device Deficiencies

All device deficiencies related to the identity, quality, durability, reliability, safety or performance of the study device shall be documented and reported through the standard commercial process. Investigators must report all possible device deficiencies associated with the device observed during the study. This includes unexpected outcomes or device deficiencies that might have led to a serious adverse event if a) suitable action had not been taken or b) intervention has not be made or c) if circumstances had been less fortunate.

Device manufacturers are required to report qualifying medical device incidents to the relevant national competent authorities. An incident is defined as “any malfunction or deterioration in the characteristics and/or performance of a device, as well as any inadequacy in the labeling or the instructions for use which, directly or indirectly, might lead to or might have led to the death of a subject or to a serious deterioration in their state of health.” A deterioration in state of health is not considered unanticipated if the condition leading to the event was considered in a risk analysis.

7.6.4 Protocol Deviation

Deviations defined in this protocol should be clearly documented, if identified during monitoring or through other means. For this study, deviations should be reported for the following categories

- Inclusion/exclusion criteria deviation(s)
- Informed Consent deviation(s)

7.7 Records Retention

The Investigator shall maintain the records associated with this study for a period of at least two years after either the date on which the investigation is completed or the date that the records are no longer required for supporting a premarket approval/notification submission, whichever is later. A Trial Master File (TMF) will be used as the master repository for all site and Sponsor regulatory documents. These records include the following:

- Correspondence with the Sponsor or designee, the Medical Monitor, and other investigators
- Subject source records, including but not limited to: Informed Consent Forms, copies of all completed CRFs, and supporting documents (laboratory reports and reports of diagnostic tests, medical records, etc.)
- All versions of study protocol
- Documentation of protocol deviations
- Reports of any serious adverse event or serious device effects
- A copy of all approvals related to the clinical investigation
- The approved, blank, informed consent form and blank CRFs
- All approval/acknowledgment letters from the IRB/EC for all versions of the study protocol, ICF and other documents
- Clinical Trial Agreement
- Signed and dated curriculum vitae for all study personnel
- Medical licenses for the Principal Investigator and all participating sub-investigators
- Financial disclosure for the Principal Investigator and all participating sub-investigators
- All required regulatory documents such as Delegation of Authority and training logs
- Signed Protocol Signature Page(s)

8. Sponsor Responsibilities

8.1 Training

The Sponsor is responsible for providing training on the protocol, CRF completion, and image upload, as applicable for all study staff per delegation of authority log.

8.2 Investigator List

The Sponsor shall keep a list of the names and addresses of the clinical Investigators for the study.

8.3 Adverse Event Reporting

The Sponsor shall evaluate adverse event reports received from the study sites and found during data monitoring and shall report them to the appropriate regulatory bodies and other study sites as necessary.

8.4 Data Monitoring

Penumbra is responsible for ensuring that the study is conducted according to the appropriate regulations (US Food and Drug Administration 21 CFR §812, ISO 14155:2011). A Penumbra employee or designate will conduct the following site visits:

8.4.1 Site Qualification Visit

Conducted to ensure the study site has the appropriate staff, facilities, and expertise to participate in the study. Site Qualification can be waived under certain circumstances.

8.4.2 Site Initiation Visit

Conducted to train the study staff on use of the device, study requirements, and other relevant training.

8.4.3 Interim Monitoring Visit

Conducted as needed to ensure the study site is operating in compliance with this protocol, continues to have the appropriate staff and facilities, and is correctly completing the CRFs.

To ensure that investigators and their staff understand and accept their defined responsibilities, the Sponsor will maintain regular correspondence and perform periodic site visits during the course of the study to verify the continued acceptability of the facilities, compliance with the study plan, and maintenance of complete records. Clinical monitoring will include review and resolution of missing or inconsistent data and source document checks to ensure the accuracy of the reported data. Informed consent, CRFs and medical records for all enrolled and screen failed subjects will be made available to the Sponsor for review and collection.

8.4.4 Site Close Out Visit

Conducted to ensure all study, device, and regulatory-related activities have been completed prior to site closure.

8.5 Data Management

Case Report Forms (CRFs) will be used at all study sites. All study data will be entered into commercially available web-based electronic data capture system (EDC). Data entry will be performed by the study site personnel. Investigators are responsible for completion and timely submission of the data to the Sponsor. Every reasonable effort should be made to complete data entry within 7 days of data collection. This EDC system requires no on-site software installation or specific hardware to operate. Investigators, clinical coordinators, data managers, and Penumbra clinical personnel access project information and study data centrally via a web browser.

Automated data quality checks will display warnings for invalid data. Additionally, manual review of data listings may be used to identify data discrepancies or inconsistencies. The study site may be queried for clarification concerning CRF discrepancies or inconsistencies identified. If CRF corrections are necessary, they will be made by the Investigator or an authorized member of the Investigator's staff that is delegated to CRF/EDC. Questions or problems with submitted data will be addressed with the Principal Investigator via an electronic querying system, or through direct contact. The Investigator will review the CRFs for completeness and accuracy and provide his/her electronic signature and date to CRFs as evidence thereof. Any data items that have been changed will require reapplication of the electronic signature.

Study personnel will have individual login and password to access the clinical study information based upon each individual's roles and responsibilities. The application provides hierarchical user permission data entry, viewing, and reporting options.

All data entry and data update information, including the date and person performing the action, will be available via the audit trail, which is part of the EDC system.

All CRFs and data files will be secured to ensure confidentiality. Investigators are required to maintain source documents required by the protocol, including laboratory results, reports, supporting medical records, and Informed Consent Forms. The source documents will be used during the regular monitoring visits to verify information entered on the CRFs.

9. Ethical Requirements

9.1 Declaration of Helsinki

The study will be performed in accordance with the applicable aspects of ISO 14155:2011, recommendations guiding physicians in biomedical research involving human subjects adopted by the 18th World Medical Assembly, Helsinki, Finland (1964 and later revisions), ICH and US FDA GCP guidelines.

It is the responsibility of the investigator to obtain approval of the study protocol from the Institutional Review Board/Ethics Committee (IRB/EC) and to keep the IRB/EC informed of any serious adverse event, serious adverse device effects, and amendments to the protocol. All correspondence with the IRB/EC should be filed by the investigator and copies sent to the Sponsor or its designee.

9.2 Informed Consent

The Investigator is responsible for ensuring that a signed and dated informed consent is obtained in accordance with Section 6.5 of this protocol, as delegated by the site-specific Delegation of Authority, and according to country and local requirements.

9.3 Subject Data Protection

Each subject will be assigned a unique subject identification number at the time of enrollment. This subject identification number will be retained throughout the study. All case report forms (CRFs) will be tracked, evaluated, and stored using only the subject ID number. No personal identifying information will be included on the case report forms.

The informed consent form will notify subjects that study monitors, auditors, and representatives of government agencies and ethics committees will have access to personal identifying information to ensure that data reported on the CRFs corresponds to the person who signed the consent form and the information contained in the source documentation. Each subject must be informed that the data collected will be stored by computer and the applicable national regulations for handling of computerized data will be followed. Furthermore, each subject should be informed about the possibility of inspection of relevant parts of the hospital records by the Sponsor, or other Health Authorities, including the FDA.

10. Statistical Procedures

10.1 General Statistical Considerations

All statistical analyses will be descriptive in nature. Descriptive statistics will include the number of observations, mean, median, standard deviation, inter-quartile range, minimum and maximum for continuous variables and counts and percentages for discrete variables. All confidence intervals presented will be two-sided. Analyses will be conducted using SAS (SAS Institute, Cary, NC). The specific details of the planned analyses will be described completely in the statistical analysis plan.

10.2 Sample Size Estimation for the Primary Outcome

Approximately 800 patients will be enrolled in this post market study with estimated 10% attrition at final follow-up. Assuming an observed rate of 89% (641/720) for the endpoint of Raymond-Roy I-II at follow-up, the sample size precision is greater than $\pm 3\%$ for this endpoint (95% CI: 87% to 91%). Assuming an observed rate of 2.8% (22/800) for the primary endpoint of device-related serious adverse events up to 7 days or discharge, the sample size precision is greater than $\pm 1.5\%$ for this endpoint (95% CI: 1.6% to 3.9%). Assuming an observed rate of 8.9% (71/800) for the primary endpoint of serious adverse events at 24 hours post procedure, the sample size precision is greater than $\pm 2.5\%$ for this endpoint (95% CI: 6.9% to 10.9%). These precision estimates are based on the normal approximation binomial 95% confidence intervals and SMART Registry interim results (data on file at sponsor). Hence, the sample size provides an adequate level of precision for these primary endpoints.

